2.2 Clinical Trial Treatments

2.2.1 Dosing Regimen

Phase Ib

- 350 mg leronlimab (PRO 140) SC weekly + AUC 5 Carboplatin every 3 weeks
- 525 mg leronlimab (PRO 140) SC weekly + AUC 5 Carboplatin every 3 weeks
- 700 mg leronlimab (PRO 140) SC weekly + AUC 5 Carboplatin every 3 weeks

Phase II

Leronlimab (PRO 140) will be administered subcutaneously at a weekly MTD dose determined in the Phase Ib portion of the study and carboplatin target of AUC 5 every 3 weeks as combination therapy until disease progression or intolerable toxicity. A de-escalation dose of carboplatin will be allowed based on the toxicity, efficacy evaluation, and clinical judgment by physician.

2.2.2 Duration of treatment:

- Pre-Screening Period: N/A (no pre-defined window period)
- **Screening Period**: Up to 4 weeks
- Treatment Period: Each treatment cycle consists of 3 weeks (21 days)
 - *Subsequent Treatment Cycles: Subjects will be eligible for continuing treatment beyond first cycle in absence of disease progression or unacceptable toxicity or withdrawal of consent
- Follow-Up Period: In both the Phase Ib and Phase II portions of the study, the follow will be done up to 2 years after treatment discontinuation or until death, whichever occurs first

2.2.3 Randomization and Stratification

Randomization and Stratification is not applicable.

2.2.4 Blinding

Blinding is not applicable.

2.3 Protocol Objective(s)

Phase Ib

Primary Objectives:

 To determine the safety, tolerability and maximum tolerate dose (MTD) of leronlimab (PRO 140) when combined with carboplatin in patients with CCR5+ mTNBC.

Secondary Objective:

• To determine the recommended Phase II dose for the combination of leronlimab (PRO 140) and carboplatin in patients with CCR5+ mTNBC.

Phase II

Primary Objective:

• To evaluate the impact on progression-free survival (PFS) of the combination leronlimab (PRO 140) and carboplatin in patients with CCR5+ mTNBC.

Secondary Objectives:

- To assess the overall response rate (ORR) and clinical benefit rate (CBR) of carboplatin leronlimab (PRO 140) combination in patients with CCR5+ mTNBC
- To assess benefit, based on time to new metastasis (TTNM)
- To assess the change in circulating tumor cells (CTCs) number after treatment; and
- To assess the safety and tolerability of the combination of leronlimab (PRO 140) and carboplatin in subjects with CCR5+ mTNBC.

2.4 Outcome Measures

2.4.1 Primary Outcome Measure

Phase Ib

 Maximum Tolerated Dose (MTD) by evaluation of dose-limiting toxicities (DLTs) of leronlimab (PRO 140) when combined with carboplatin AUC5.

Note: The MTD is defined as 1 dose level below the dose in which dose limiting toxicities (DLTs) were observed in $\geq 33\%$ of the participants during Cycle 1.

Phase II

• Progression free survival (PFS) defined as time in months from the date of first study treatment to the date of disease progression or death from any cause, whichever comes first.

Note: All patients who receive at least one dose of leronlimab (PRO 140) and carboplatin combination will be included in the primary analyses of PFS. The Response Evaluation Criteria in Solid Tumors (RECIST v1.1) criteria will be used for objective tumor response assessment (when disease is measurable and non-measurable);

The time in months from start of treatment to progression or death will be measured for all patients who receive at least one dose of study drug. Patients will be followed up to 2 years after completion of treatment.

2.4.2 Secondary Outcome Measures

Phase Ib

• The number, frequency, and severity of adverse events (AEs) collected from the time of first treatment until 12 weeks after study treatment completion to evaluate safety of leronlimab (PRO 140) and carboplatin in subjects with CCR5+ mTNBC.

Note: Adverse events will follow National Cancer Institute Common Terminology Criteria for Adverse Events (CTCAE) version 5.0

Phase II

 PFS according to RECIST v1.1 in participants with Detectable Programmed Death-Ligand 1 (PD-L1)

Note: The PD-L1 expression testing will be performed at baseline. Breast tissue (primary or metastatic site) collected to analyze for the presence of CCR5 at pre-screening will additionally be used for evaluating PD-L1 expression levels.

• Overall response rate (ORR, defined as Complete Response (CR) + Partial Response (PR)), and clinical benefit rate (CBR, defined as CR + PR + Stable Disease (SD)) in subjects with CCR5+ mTNBC treated with leronlimab (PRO 140) and carboplatin.

Note: Overall response rate defined as the proportion of patients who achieve an overall response of complete response or partial response in the total number of evaluable patients, assessed by RECIST v1.1. Clinical benefit rate is defined as the proportion of patients who achieve an overall response of complete response or partial response or stable disease in the total number of evaluable patients, assessed by RECIST v1.1. Imaging scans to be done at the end of 2 cycles (i.e., every 6 weeks) for the first 6 cycles (18 weeks) and at the end of 3 cycles (i.e., every 9 weeks) thereafter.

- Time to new metastases (TTNM);
 - Note: Recorded time from baseline metastatic disease (at time of enrollment) to the time of development of new metastasis in different site. New metastases in same site will be also recorded.
- The change from baseline in circulating tumor cells (CTC) level in the peripheral blood.

 Note: Reported unit of measure will be the number of CTCs/milliliter. CTCs enumeration will be performed at baseline and at the time of response assessment. Fraction of baseline positive and change from ≥5 CTCs will be recorded and reported.

Protocol: CD07_TNBC CytoDyn, Inc.

• Overall survival defined as time in months from the date of first study treatment to the date of death;

Note: Patients will be followed from the start of treatment until 2 years post-treatment or death, whichever occurs first, and average survival time will be measured.

• The number, frequency, and severity of AEs collected from the time of first treatment until 12 weeks after study treatment completion to evaluate safety of leronlimab (PRO 140) and Carboplatin in subjects with CCR5+ mTNBC.

2.4.3 Exploratory Outcome Measures

- Measure immune biomarkers (PD-L1) in CTCs, metastatic tissue and immune cells such as CAMLs and correlate with therapeutic benefit (PFS); and
- Correlation between CCR5 expression (CTCs, CAMLs) and PD- L1 expression.

2.5 Safety Assessments

Safety will be assessed by close monitoring and timely assessment of adverse events (AEs), laboratory parameters (blood tests, urinalysis), vital signs (blood pressure, heart rate), subject's medical condition (physical examination including weight), general well-being and activities of daily life (Eastern Cooperative Oncology Group (ECOG) performance status). Each subject will be regularly assessed in each cycle for potential AEs and disease related signs and symptoms. The CTCAE v5.0 will be used to grade toxicities/AEs.

3. SAMPLE SIZE DETERMINATION

This is a Phase Ib/II, multicenter study that will enroll up to 18 subjects in Phase Ib and 30 subjects in Phase II of the study. The sample size for Phase Ib is based on conventional 3+3 study design and Phase II is based on clinical judgment. No statistical power calculation is used to establish the sample size.

4. INTERIM ANALYSIS/DSMB

No interim analysis (IA) will be performed for efficacy. There will be a safety review, once all three (or six) subjects from each cohort complete the DLT evaluation period (defined as cycle 1 or the first 21 days of treatment).

The Sponsor's Medical Monitor, CRO Medical Monitor and study investigators must be satisfied with data obtained in Cohort A before allowing subsequent enrollment of Cohort B. Likewise, they

must be satisfied with data obtained in Cohort B before allowing subsequent enrollment in Cohort C.

In addition, should any of the following events occur in any cohort during the DLT evaluation period, the Data Safety Monitoring Board (DSMB) will meet to review available study data and make a final decision for dose escalation to the next cohort:

- a. Death in any subject in which the cause of death is judged to be possibly, probably or definitely related to leronlimab (PRO 140)
- b. The occurrence in any subject of an anaphylactic reaction to leronlimab (PRO 140)
- c. The occurrence in any subject of a severe local injection site reaction (Grade 3 which is not resolved or recurs; or Grade 4) that precludes administration of consecutive leronlimab (PRO 140) doses.
- d. The occurrence in any subject of a life-threatening SAE whose causal relationship to leronlimab (PRO 140) is judged to be probable or definite
- e. The occurrence of one or more non-life-threatening SAEs whose causal relationship to leronlimab (PRO 140) is judged to be definite
- f. The occurrence, in one or more subjects, of Grade 4 laboratory abnormalities, judged to be probably or definitely related to receipt of leronlimab (PRO 140)
- g. The occurrence of hematologic and non-hematological adverse events, judged to be possibly, probably or definitely related to receipt of leronlimab (PRO 140) based on previous clinical experience and that are of CTCAE Grade 3 or greater severity. Permissible exceptions to this rule include Grade 3 fatigue of less than one week duration, and Grade 3 nausea, vomiting, and diarrhea that resolve within 48 hours following institution of appropriate supportive care.
- h. Hy's law
- i. Neutropenic fever
- j. Grade 4+ neutropenia or thrombocytopenia >7 days
- k. Grade 3+ thrombocytopenia with bleeding
- 1. Grade 3+ electrolyte abnormality that lasts >72 hours, unless the patient has clinical symptoms, in which case all grade 3+ electrolyte abnormality regardless of duration should count as a DLT. Grade 3+ amylase or lipase elevation NOT associated with symptoms or clinical manifestations of pancreatitis does not need to be counted as a DLT

Protocol: CD07_TNBC CytoDyn, Inc.

m. For patients with hepatic metastases, AST or ALT >8xULN or AST or ALT >5x ULN for ≥ 14 days.

5. HYPOTHESIS TO BE TESTED

There is no formal hypothesis testing for this study as the study is an initial Phase Ib/II evaluation and is intended to be hypothesis generating. The study is not powered to reliably yield statistically significant conclusions.

6. ANALYSIS POPULATIONS

6.1.1 Intent-to-Treat (ITT) Population

The ITT population is defined as the set of subjects who have received at least one dose of leronlimab (PRO 140) and have measurable disease at baseline. The ITT population will be used as the primary analysis population.

6.1.2 Per Protocol (PP) population

The Per Protocol (PP) population is defined as the set of subjects who meet the ITT population requirements, were not associated with any major protocol violations and have received at least 2 cycles of treatment. This population will be identified before the database lock. The PP analysis of primary and secondary outcome measures will be considered supportive.

6.1.3 Safety Population

The Safety Population will include all subjects who have received one dose of leronlimab (PRO 140). This population will be used for the analysis of safety parameters or measurements.

7. DATA CONVENTION AND RELATED DEFINITIONS

7.1 Baseline Definition

For all parameters, baseline will be defined as the last available value before the first treatment.

7.2 Duplicate Data

For unplanned duplicate data within a protocol-specified visit duration, the last measured value will be used for the analysis. If it is not possible to identify the "last measured value" the average of the duplicate values will be used.

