- [25] Can be performed within 3 days prior to each cycle start.

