7.11 CLINICAL LABORATORY ASSESSMENTS

Blood samples will be collected for analysis of the following parameters:

- Biochemistry and Complete Blood Count (CBC) Parameters: At Screening and Day 1 of each treatment cycle and at the end of treatment (EOT).
- Serum pregnancy test (for female subjects of childbearing potential): At Screening
- Urine pregnancy test (for female subjects of childbearing potential): At Day 1 of each treatment cycle
- CTCs PD-L1/CCR5 Analysis: At Day 1 of each treatment cycle and at the end of treatment (EOT).
- CTC and CAMLs Analysis: At Day 1 of each treatment cycle and at the end of treatment (EOT).

All laboratory reports will be reviewed by the Investigator. Abnormal results that are considered by the Investigator to be clinically significant, will be recorded as adverse events. If in the Investigator's judgment, in order to make the determination of clinical significance the testing may be needed to be repeated. Validated, quality-controlled laboratory data will be transferred to the main database for analyses.

Table 7-2: Central Lab Parameters

CBC Parameters	Biochemistry Parameters	Urinalysis
Hemoglobin	Liver Function Tests	pH
Hematocrit	Total Bilirubin	Appearance
RBC count	Direct Bilirubin	Color
WBC count	Alkaline Phosphatase (ALP)	Specific gravity
WBC Differential	Alanine Aminotransferase (ALT) (or SGPT)	Turbidity
Absolute lymphocyte count	Aspartate Aminotransferase (AST) (or SGOT)	Ketones
Absolute neutrophil count	Albumin	Bilirubin
Platelet count	Total Protein	Blood
Miscellaneous		Glucose
Serum pregnancy test	Renal Function Tests	Protein
Urine pregnancy test	blood urea nitrogen (BUN)	Nitrites
(for female subjects of childbearing potential)	Creatinine	Urobilinogen
Tissue for CCR5 expression (archival or fresh biopsy)	Electrolytes	Leukocyte esterases
Tissue for PD-L1 expression (archival or fresh biopsy)	Sodium	Microscopic exam includes bacteria, cast, crystals, epithelial cells, RBC and WBC.
CTCs PD-L1/CCR5	Potassium	
CTC CAMLs	Chloride	
	Calcium	
	Bicarbonate	
	Other:	
	Glucose, Random, Serum	

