8.4.3.2 Individual Patient Changes

Laboratory data will be classified into grades according to DAIDS toxicity grading. A severity grade of 0 will be assigned when the value is within normal limits.

The following summaries will be produced for the hematology and biochemistry laboratory data (by laboratory parameter):

- Shift tables using DAIDS grades to compare baseline to the worst post-baseline value will be produced for hematology and biochemistry laboratory parameters with DAIDS grades
- Shift tables using Low/High/Normal relative to the laboratory reference ranges to compare baseline to the worst post-baseline value will be produced for hematology and biochemistry laboratory parameters without DAIDS grades

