8.4.4.2 Clinically notable below normal values

• Systolic BP: \leq 90 mmHg and a decrease \geq 20 mmHg from baseline

• Diastolic BP: ≤ 50 mmHg and a decrease ≥ 15 mmHg from baseline

• Body temperature: ≤ 35°C

• Heart rate: ≤ 50 bpm with decrease from baseline of ≥ 15 bpm

 Respiration rate: < 8 breaths per minute with decrease from baseline of ≥ 6 breaths per minute

Number and percentage of patients with at least one post-baseline vital sign abnormality (in both directions, i.e. both elevated and below normal values) will be summarized by treatment group.

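### SAP 7.2 keeps only the last or averaged duplicate value in a visit and is not reconciled with the worst-value safety tables, so laboratory toxicity can be understated

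*SAP*

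**What the plan says.** SAP 7.2 is one of the general data conventions in Section 7. For unplanned duplicates within a visit, it says that "the last measured value will be used for the analysis". Where the last value cannot be identified, "the average of the duplicate values will be used". No data type is exempted, and the length of a visit is not defined.

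The safety sections ask for something different:

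- SAP 8.4.3.2, haematology and biochemistry: "Shift tables using DAIDS grades to compare baseline to the worst post-baseline value will be produced". Parameters without DAIDS grades get a parallel low/normal/high table, also on the worst value.
- SAP 8.4.4.2: "Number and percentage of patients with at least one post-baseline vital sign abnormality".
- SAP 8.4.5: subjects with one or more notable ECG changes, with the PR, QRS and ventricular-rate criteria applied to every assessment after baseline.

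Two Protocol provisions bear on how duplicates arise. Section 7.11 says of abnormal laboratory results that "in order to make the determination of clinical significance the testing may be needed to be repeated". Footnote 25 to Table 4-1, on the cycle bloods and urinalysis, says: "Can be performed within 3 days prior to each cycle start".

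**The concern.** A worst-value table is only as good as the set of values searched. If the dataset is first reduced to one value per visit under SAP 7.2, the worst value is sought among survivors of a rule that ignores severity. For laboratory tests the repeats are not a random subset, because the Protocol's stated reason for repeating is to interpret an abnormal result. Such a repeat will tend to be milder than the value that prompted it, through recovery or regression to the mean. Averaging also dilutes the extreme.

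Safety and tolerability is a Phase Ib primary and a Phase II secondary objective, and Protocol 1.3.2 names marrow suppression as carboplatin's dose-limiting toxicity. With 30 Phase II patients, one patient moved out of a severe grade changes the rate by 1/30 = 3.3 percentage points. SAP 7.4 plans no sensitivity analysis that would reveal the loss.

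**Working it through.** The documents state no abnormality, repeat or recovery rate, so there is no figure of the plan's to reproduce. The check has two parts.

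**1. Order of operations.** Take a post-baseline cycle visit with a Grade 3 or higher value from an early draw and a milder recheck before dosing, both assigned to that Day 1 visit.

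- SAP 7.2 applied first: only the recheck (or the average) remains, and the higher value never reaches the shift table.
- SAP 8.4.3.2 applied to all recorded values: the higher value is the worst value and is counted.

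Both routes fit the text, and the SAP does not choose between them. Cycle 1 Day 1 pre-dose bloods are not exposed, because under SAP 7.1 values before first treatment are baseline. Exposure starts at Cycle 2 Day 1.

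**2. Illustration of size.** All three inputs are assumptions:

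- K = number of post-baseline laboratory visits;
- p = probability per visit that the first value is Grade 3 or higher;
- d = probability that such a value is repeated in the same visit window and the repeat is below Grade 3.

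Visits are treated as independent, and repeats that turn out worse are ignored. The proportion of patients with a worst grade of 3 or more is

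- all values: 1 − (1 − p)^K
- last value per visit: 1 − (1 − p(1 − d))^K

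With K = 6 and p = 0.05, all values give 1 − 0.95^6 = 26.5%, or 7.9 of 30 patients. Last value only gives:

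| d | Calculation | Proportion | Of 30 | Shortfall (points) |
|---|---|---|---|---|
| 0.10 | 1 − 0.955^6 | 24.1% | 7.2 | 2.4 |
| 0.25 | 1 − 0.9625^6 | 20.5% | 6.1 | 6.0 |
| 0.50 | 1 − 0.975^6 | 14.1% | 4.2 | 12.4 |

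Over K = 4 to 8, p = 0.02 to 0.10 and d = 0.10 to 0.50, the shortfall runs from 0.8 points (K = 4, p = 0.02, d = 0.10) to 23.3 points (K = 8, p = 0.10, d = 0.50). It is zero if d = 0 or if the worst value is taken over everything recorded.

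**The case against.** The strongest reply is that a specific rule overrides a general one: worst post-baseline value in SAP 8.4.3.2 can be read as covering every recorded value, and then nothing is lost. That reading is available but nowhere stated, and SAP 7.2 as worded points the other way for duplicates.

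Other parts of the case limit the point and stand:

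- SAP 7.2 covers only duplicates within a protocol-specified visit. The weekly blood counts that Protocol Table 6-4 requires during some haematologic holds, and off-schedule returns treated as unscheduled visits under Protocol 4.5, may fall outside it and so stay in the worst-value search.
- Footnote 25 permits an early draw; it does not call for a second one.
- By its wording the rule has no direction: a later, worse repeat would be kept. The downward tendency comes from why repeats are taken.

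A further reply is that the adverse event tables catch these cases, since clinically significant abnormalities are recorded as AEs and SAP 8.4.1 takes the worst severity. This holds only in part. The repeat helps to decide clinical significance, and Protocol 9.1 says findings judged not significant are not recorded as AEs. SAP 8.4.3.4 lists only abnormalities that became AEs. A recovered repeat can thus keep a value out of the AE tables as well as the shift table, leaving it only in the by-subject listing.

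A reader might infer that the rule does lower the reported toxicity rates, for vital signs as much as for laboratory values, and that it touches the Phase Ib dose decision. The documents do not support that. Repeats are described for laboratory tests only, and as something that may be needed. No section describes repeating vital signs because they were abnormal; the pre- and post-injection readings in SAP 8.4.2.2 are planned pairs. DLTs are judged on observed events, not on a value selected under SAP 7.2.

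**Conclusion.** The point holds as a conditional one. SAP 7.2 has no safety exception and is not reconciled with the worst-value and any-abnormality tables. Applied first, it can drop an abnormal laboratory value in favour of a milder repeat and so can understate laboratory toxicity in the shift tables. That is firm from the text. The size cannot be determined from the documents: the 0.8 to 23.3 points above rest wholly on assumed K, p and d, and the effect is zero under the other reading.

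The reach is limited to laboratory shift tables, by-visit summaries and possibly the vital-sign and ECG any-abnormality counts, the last only through the generality of SAP 7.2. DLT and MTD decisions and the by-subject listings are unaffected, and AE tables at most indirectly. It should be corrected because the ambiguity falls on a summary that is meant not to depend on investigator judgment.

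**What to change.** Restrict SAP 7.2 to by-visit summaries, and add a sentence to this effect: worst-grade, shift and any-abnormality safety tables in SAP 8.4.3 to 8.4.5 use all post-baseline values, including repeat and unscheduled ones, and no value is replaced by a later repeat or by an average. Baseline stays as SAP 7.1 defines it.

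This needs no new data collection, since all laboratory results are already to be listed by subject. The cost is a short SAP edit before the tables are programmed, and reported toxicity rates that may be slightly higher.

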7.3 Handling of Missing Data

All data will be used as observed, and no imputations will be made for any missing data point. All summaries will be based on observed data only.

7.4 Sensitivity Analysis

There will be no sensitivity analysis for this Phase Ib/II study.

7.5 Multicenter Clinical Trials

This is a multi-center clinical trial.

7.6 Multiple Comparisons and Multiplicity

There will be no adjustment for any multiple comparisons for this Phase Ib/II study.

7.7 Covariates and Prognostic Factors

No covariates are planned for this study.

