Due to its low rates of adverse events and unique mechanism of action, carboplatin has been combined with a variety of chemotherapy agents and targeted therapies such as taxanes, gemcitabine, trastuzumab, pertuzumab, bevacizumab and PARP inhibitors [Lalezari, 2005][Landovitz, 2008] [Suleiman, 2010][Cooper, 2010][Cooper, 2014] [Fatkenheuer, 2008]. Recent data have shown that in patients with TNBC, first line monotherapy with carboplatin presented similar results in RR, PFS and OS when compared to the standard arm docetaxel in a phase III trial. Moreover, in this trial patients with TNBC harboring BRCA mutation presented superior response rate, PFS and OS survival when compared to the docetaxel arm [Guilick, 2014].

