1.5 RATIONALE FOR TARGET POPULATION AND DOSE SELECTION

Triple-negative breast cancer (TNBC), defined clinically as tumors that do not express estrogen receptors (ER), progesterone receptors (PgR), or Her-2, remains a major therapeutic challenge due to the lack of available targeted agents and the high risk of disease recurrence [Dawood, 2011][Engstrom, 2013]. Although anthracyclines and taxanes are the most active agents, most will require other chemotherapy options, particularly carboplatin. TNBC is associated with a higher incidence of visceral metastasis as site of first-recurrence compared to other disease subtypes. Following recurrence, TNBC patients fare less well than their non-TNBC counterparts, with a median response duration to first-line palliative therapy of only 3 month, a median PFS of 5 months and a median survival of 9–12 months [Dawood, 2011][Harbeck, 2016][Malorni, 2012]. PFS has been considered an adequate endpoint in this population when evaluating the role of biological agents including PARP-inhibitors and antiangiogenic agents such as bevacizumab.

Metastasis is the primary cause of death in patients with breast cancer. Currently no treatments exist that are directed specifically to the metastatic process. The current proposal provides strong preliminary evidence that: 1) a receptor, CCR5, is expressed in a subset of human breast cancer, 2) CCR5 is intrinsically related to invasiveness and metastasis cascade, 3) CCR5 is associated with upregulation of PD-L1 and the adaptative immune system process of tumor evasion, 4) CCR5 correlates with DNA repair activities. Furthermore, CCR5 inhibitors, previously developed and FDA approved for treatment of HIV patients, can effectively block breast cancer metastasis in preclinical models. The repurposing of drugs for alternative use in cancer metastasis, drugs that were previously approved by the FDA, may provide a more rapid solution for this deadly disease. We hypothesize that the combination of the CCR5 antagonist leronlimab (PRO 140) with the platinum agent carboplatin will: 1) Increase PFS due to both carboplatin and leronlimab (PRO 140) antitumor efficacy and reduced burden of metastasis secondary to CCR5 blockage by leronlimab (PRO 140); 2) Increase overall response rate due to an expected synergy in DNA crosslink strand break of carboplatin and reduce DNA repair secondary to CCR5 blockage by leronlimab (PRO

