8.6.2. Covariates

For efficacy analyses, the baseline values will be used as covariates in the analysis models. Other important prognostic factors will be specified in the SAP for the study.

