7.8 Stratification Factors and Subgroups

There are no stratification factors or subgroups for this trial.

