8.1.3 Demographics and Other Baseline Characteristics

Demographics (age, race, gender, ethnicity), height, weight will be listed and summarized descriptively. See Section 7.1 for baseline definition.

Medical history findings will be provided as by-subject listings.

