8.3 Analysis of Secondary Outcome Measures

8.3.1 PFS according to RECIST v1.1 in participants with Detectable Programmed Death-Ligand 1 (PD-L1)

PFS according to RECIST v1.1 in participants with Detectable Programmed Death-Ligand 1 (PD-L1) will be calculated using Kaplan-Meier curves, and the median PFS will be read from this curve. Note: The PD-L1 expression testing will be performed at baseline. Breast tissue (primary or metastatic site) collected to analyze for the presence of CCR5 at pre-screening will additionally be used for evaluating PD-L1 expression levels.

8.3.2 Overall response rate (ORR) and clinical benefit rate (CBR) in subjects with CCR5+ mTNBC treated with leronlimab (PRO 140) and carboplatin

Overall response rate (ORR) and clinical benefit rate (CBR) in subjects with CCR5+ mTNBC treated with leronlimab (PRO 140) and carboplatin will be calculated using proportions and 95% confidence intervals.

Note: Overall response rate defined as the proportion of patients who achieve an overall response of complete response or partial response in the total number of evaluable patients, assessed by RECIST v1.1. Clinical benefit rate is defined as the proportion of patients who achieve an overall response of complete response or partial response or stable disease in the total number of evaluable patients, assessed by RECIST v1.1. Imaging scans to be done at the end of 2 cycles (i.e., every 6 weeks) for the first 6 cycles (18 weeks) and at the end of 3 cycles (i.e., every 9 weeks) thereafter.

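### SAP 7.7 and 7.8 contradict Protocol 8.6.2 and SAP 8.3.1, and Phase II PFS is pooled over two lines of therapy although the only reference figure, about 5 months, describes one of them

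*SAP*

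**What the plan says.** **Covariates.** Protocol 8.6.2 states "For efficacy analyses, the baseline values will be used as covariates in the analysis models" and adds "Other important prognostic factors will be specified in the SAP for the study". SAP 7.7 says "No covariates are planned for this study", and the SAP names no prognostic factor elsewhere.

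**Subgroups.** SAP 7.8 says "There are no stratification factors or subgroups for this trial". SAP 8.3.1 then plans a subgroup analysis: "PFS according to RECIST v1.1 in participants with Detectable Programmed Death-Ligand 1 (PD-L1) will be calculated using Kaplan-Meier curves".

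**Baseline description.** Protocol 7.3 collects year of diagnosis, morphology, histologic grade, BRCA1/2 status, menstrual status and location of metastasis. Protocol 8.7.2 says such characteristics will be listed, summarised or both. SAP 8.1.3 says "Demographics (age, race, gender, ethnicity), height, weight will be listed and summarized descriptively", with medical history as by-subject listings. The assessment schedules differ in the same way: the protocol's row covers demographics and baseline disease characteristics, the SAP's row demographics only. The protocol's medical-history footnote includes prior anti-tumoral therapy for breast cancer; the SAP's footnote does not.

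**PFS and its reference.** SAP 8.2.2 plans one Kaplan-Meier curve with its median and names no confidence interval. Protocol 1.5 gives "median response duration to first-line palliative therapy of only 3 month, a median PFS of 5 months". Protocol 3 and SAP 2.1 attach the 5 months to newly recurred disease.

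**Population.** Phase II inclusion criterion 5 (Protocol 3.3.1) admits first-line patients and also patients who failed first-line chemotherapy combined with a checkpoint inhibitor in the metastatic setting.

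**The concern.** Phase II has no control arm, so the natural reading of its result is whether median PFS lies above or below 5 months. SAP 2.1 invites that reading: it says the phase examines whether the combination increases PFS and gives the 5-month figure in the next sentence. The figure does not describe the previously treated patients whom the same trial admits. If they progress sooner, their share pulls the pooled median down whatever leronlimab does.

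Followed as written, the SAP gives one pooled median, no split by line and no specified summary of prior treatment. A real gain could look like no gain, and a shortfall could be put down to the drug when it reflects who was enrolled. The contradictory clauses also leave the analyst without a rule: one document requires covariates, the other excludes them, and the exclusion of subgroups is broken by a planned secondary analysis.

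**Working it through.** **The plan's own figures.** N = 30 rests on clinical judgment, with no alpha, power or effect size (SAP 3), so there is nothing to reproduce for Phase II. The Phase Ib maximum does reproduce: 3 dose levels × 6 = 18.

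**Inputs for the mixture.**
- First-line median: 5 months (Protocol 1.5 and 3; SAP 2.1).
- Post-first-line median m: not in the documents. Assumed 3 months, range 2 to 4. The 3 months in Protocol 1.5 is a response duration and is not the source.
- Share w of post-first-line patients: not in the documents. Shown at 25, 50 and 75%.
- Exponential PFS in each group, no leronlimab effect.

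**Formula.** The pooled median t solves

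(1 − w) × 0.5^(t/5) + w × 0.5^(t/m) = 0.5

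Check at w = 0.5, m = 3, t = 3.83: 0.5 × 0.588 + 0.5 × 0.413 = 0.50.

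| Assumed m (months) | w = 25% | w = 50% | w = 75% |
|---|---|---|---|
| 2 | 3.92 | 3.06 | 2.44 |
| 3 | 4.37 | 3.83 | 3.38 |
| 4 | 4.72 | 4.46 | 4.22 |

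With no drug effect, the pooled median falls below 5 by 0.3 months (5 − 4.72) to 2.6 months (5 − 2.44).

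**A real effect hidden.** Suppose both lines gain 1.5-fold: 5 × 1.5 = 7.5 and 3 × 1.5 = 4.5 months. All the times scale by 1.5, so the pooled median is 3.83 × 1.5 = 5.75 at w = 50% and 3.38 × 1.5 = 5.07 at w = 75%. The second is almost equal to the reference.

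**Chance that the observed median exceeds 5.** Simulating 30 uncensored patients (40,000 replicates):
- all first-line, no effect: about 50%;
- 50:50 mix of 5 and 3 months, no effect: about 15%;
- 75% post-first-line with the 1.5-fold gain: about 52%.

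A trial with a 1.5-fold effect and many pretreated patients thus looks much like one with no effect and none.

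**Precision.** On the log scale the 95% limits are the median × exp(±1.96/√d) for d events. A median of 5 with d = 30 gives 3.5 to 7.2. For a subgroup with d = 15, exp(1.96/√15) = 1.66.

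**The case against.** Much can be said for the plan, and most of it limits the point without removing it.

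- **No formal comparison is planned.** SAP 5 calls the study hypothesis generating, and SAP 8.2.2 does not test PFS against 5 months. This stands: the comparison is informal. It is still the only yardstick the documents offer.
- **Covariates would not repair the primary result.** Protocol 8.7.3.1 uses the same pooled Kaplan-Meier median, which takes no covariates. This stands: a reader might infer that SAP 7.7 causes the pooling, but restoring Protocol 8.6.2 would leave the median unchanged. The clause conflict and the pooling need separate remedies.
- **Case mix is not hidden.** A reader might infer that the SAP withholds it or drops a promised table. Protocol 8.7.2 accepts a listing in place of a summary, SAP 8 puts all data in listings, and SAP 12.1 and 12.2 keep general headings for baseline characteristics. Counts for 30 patients could be taken from listings. The gap is that the disease variables are not named for summary.
- **Sampling error is large.** At the central assumption only the 75% case (3.4 months) falls outside 3.5 to 7.2. That is fair, but an interval around a pooled median does not show a shift caused by case mix.

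A stronger reading concerns BRCA. Protocol 1.3.2 says "patients with TNBC harboring BRCA mutation presented superior response rate, PFS and OS survival", and a reader might infer that carriers would lift the median above 5 months. The documents do not support a size for this. That sentence compares carboplatin with docetaxel among carriers, not carriers with non-carriers on carboplatin. Nor does the 5-month figure exclude carriers, so only a difference in carrier share between the trial and the reference population would matter.

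**Conclusion.** The point holds as a low-cost improvement. Two contradictions are plain on the text: SAP 7.7 against Protocol 8.6.2, and SAP 7.8 against SAP 8.3.1. SAP 8.1.3 also leaves the baseline disease variables unspecified.

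The pooled Phase II median cannot be read against 5 months without the line mix. At an assumed post-first-line median of 3 months it would be 4.4, 3.8 or 3.4 months with no drug effect at 25, 50 or 75% such patients; across all assumptions shown the range is 2.4 to 4.7. These sizes rest on exponential PFS and on shares and a post-first-line median that the documents do not give. The direction needs only that previously treated patients progress sooner than first-line patients. No magnitude is claimed for BRCA status.

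**What to change.** 1. **Reconcile the clauses.** Make SAP 7.7 and Protocol 8.6.2 agree on whether covariates are used, in which models, and which prognostic factors count. Amend SAP 7.8 to acknowledge the PD-L1 analysis in 8.3.1 and the split by line below.
2. **SAP 8.1.3.** Summarise line of therapy, prior checkpoint inhibitor, prior neoadjuvant or adjuvant carboplatin, BRCA1/2 status, histologic grade and metastatic site.
3. **SAP 8.2.2 and 8.3.2.** Report median PFS (Kaplan-Meier, 95% CI) and ORR descriptively for first-line and for post-chemotherapy/checkpoint patients separately. Cite 5 months only beside the first-line group. A descriptive PFS split by BRCA status may be added, since the status is collected.

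**Cost.** SAP text and a few tables from data already collected. Line of therapy is not in the Protocol 7.3 list, so one rule is needed to derive it from the prior anti-tumoral therapy recorded under Protocol 7.4. The groups will be small: with 15 events the 95% interval runs from the median divided by about 1.66 to the median multiplied by about 1.66, so the split describes the patients and should not be used to compare the lines.
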